6.5. Dose Modification

Titration and optimization of study intervention dose during the Dose Titration and Optimization Period will occur as outlined in [Section 4.1](#). During the Maintenance Period, participants will take suvecaltamide or placebo at the optimal dose determined by the investigator at the end of the Dose Titration and Optimization Period (10, 20, or 30 mg once daily). No dose adjustment should occur during the Maintenance Period. If the investigator determines a dose adjustment is indicated for safety reasons, the Medical Monitor should be consulted regarding continuation of study intervention.

6.6. Continued Access to Study Intervention after the End of the Study

There is no continued access to study intervention upon completion of the study. Participants should follow-up with their healthcare provider regarding PD medications following study participation.

6.7. Treatment of Overdose, Medication Errors, or Misuse

For this study, any dose of suvecaltamide (or placebo) greater than the assigned dose that a given participant takes within a 24-hour period will be considered an overdose. In case of an acute overdose, it is recommended that the stomach is emptied and that oral gavage with activated charcoal is used to reduce absorption of suvecaltamide. Attendant signs and symptoms should be managed expectantly. See the IB for details.

In the event of an overdose, the investigator should:

- Contact the Medical Monitor immediately.
- Evaluate the participant to determine, in consultation with the Medical Monitor, whether study intervention should be interrupted or discontinued.
- Closely monitor the participant for any AE/SAE and/or laboratory abnormality.
- Document the quantity of the excess dose as well as the duration of the overdose.

[figure not shown]
6.8. Concomitant Therapy

Any medication or vaccine (including over-the-counter or prescription medicines, recreational drugs, vitamins, and/or herbal supplements) that the participant is receiving at the time of enrollment or receives during the study must be recorded along with:

- Reason for use;
- Dates of administration including start and end dates; and
- Dosage information including dose and frequency.

Concomitant treatment with certain medications/therapies is not permitted during the study (see [Section 5.2](#)).

Participants will continue their permitted PD medication(s) at the same stable dose(s) and regimen(s) as in the 6 weeks immediately prior to the study and will remain on the same dose(s) and regimen(s) of these medication(s) until the end of the study. On clinic visit days, site staff will record the time of the last dose(s) of PD medication(s) prior to the efficacy assessments. For all participants, efficacy assessments should occur during “ON” periods, as determined by the investigator, in relation to the participant’s PD medication(s).

Refer to the permitted, prohibited, and cautionary list of medications in the Trial Site Binder.

The Medical Monitor should be contacted if there are any questions regarding concomitant or prior therapy.

7. DISCONTINUATION OF STUDY INTERVENTION AND PARTICIPANT DISCONTINUATION/WITHDRAWAL

7.1. Discontinuation of Study Intervention

In some instances, it may be necessary for a participant to permanently discontinue study intervention.

A participant **must** be discontinued from study intervention for any of the following reasons:

- The participant or their legally authorized representative requests to discontinue study intervention.
- The participant has an AE that may compromise the participant's continued participation.
- The participant has a suicide risk reported or assessed by the C-SSRS (see [Section 8.3.6](#)).
- The participant has a positive serum pregnancy test ([Appendix 5](#) and [Section 8.4.5](#)).
- The participant is noncompliant with study intervention or procedures.
- The sponsor decides to terminate the study prior to completion.
- The investigator determines the participant should not continue study intervention.

7.1.1. Participants Remaining in the Study After Study Intervention Discontinuation

Discontinuation from study intervention does not represent discontinuation from the study. For participants who discontinue study intervention early, every effort should be made to attend Efficacy Follow-up Visits through 17 weeks after the first dose of study intervention. After completing the E/D visit, if the participant is willing to attend Efficacy Follow-up Visits after the study intervention is discontinued, the guidelines for scheduling efficacy visits are as follows:

- For participants who discontinue study intervention prior to the Week 9 Visit, it is encouraged to schedule 3 additional Efficacy Follow-up Visits at 9, 13, and 17 weeks after first dose.
- For participants who discontinue study intervention after the Week 9 Visit but prior to the Week 13 visit, it is encouraged to schedule 2 additional Efficacy Follow-up Visits at 13 and 17 weeks after first dose.
- For participants who discontinue study intervention after the Week 13 Visit but prior to the Week 17 Visit, it is encouraged to schedule an additional Efficacy Follow-up Visit at 17 weeks after first dose.
- Participants should be scheduled for the Safety Follow-up Visit 2 weeks after the last dose of study intervention. However, 1 of the Efficacy Follow-up Visits can be combined with the participant's Safety Follow-up Visit if the Efficacy Follow-up Visit is scheduled to occur within 2 weeks after the participant's last dose of study intervention.

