[REDACTED] SV = Screening Visit; TETRAS-ADL = The Essential Tremor Rating Scale, Activities of Daily Living Subscale; TETRAS-PS = The Essential Tremor Rating Scale, Performance Subscale; W = week; WOCBP = women of childbearing potential.

^a Discontinuation from study intervention does not represent discontinuation from the study. For participants who discontinue study intervention early, every effort should be made to attend Efficacy Follow-up Visits through 17 weeks after the first dose. See [Section 7](#) for additional guidance.

^b If participant discontinues study intervention early (regardless of whether or not he/she continues in the study), he/she will require an E/D Visit and a Safety FU Visit. The E/D Visit should occur as soon as possible following early discontinuation of study intervention. The Safety FU Visit should occur 2 weeks after the E/D visit.

^c Additional onsite clinic visits may be scheduled at any time, including in place of scheduled phone contacts, if required due to local requirements (eg, for study intervention dispensation). If performed in-clinic, urine pregnancy testing should be completed for WOCBP.

^d Clinic visits at Week 1, Week 2, Week 5, Week 9, Week 13, E/D, and Safety FU may be conducted remotely, if required due to the coronavirus 2019 pandemic, and with approval from the Sponsor Medical Monitor. The TETRAS-PS and MDS-UPDRS will not be performed during remote visits [REDACTED]
[REDACTED]

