[REDACTED] [REDACTED]. If needed, participants will be able to titrate down to a minimum of 10 mg suvecaltamide (or a minimum of 1 matching placebo capsule) per day at any time following consultation with the investigator. Participants not tolerating a once-daily dose of 5 mg suvecaltamide after 2 weeks of treatment will be discontinued from the study.

- Maintenance Period: participants will continue to take study intervention of 1, 2, or 3 capsules of either suvecaltamide (10 mg per capsule) or matching placebo at the optimal dose determined by the investigator at the end of the Dose Titration and

Optimization Period (see [Table 7](#)). No dose adjustment should occur during the Maintenance Period. If the investigator determines a dose adjustment is indicated for safety reasons, the Medical Monitor should be consulted regarding continuation of study intervention.

A 2-week Safety Follow-up Period (with visit planned at the end of the 2-week period) will be required for participants who either discontinue early or fully complete the Maintenance Period.

Assessments of efficacy, safety, [REDACTED] will be conducted as described in [Section 8.2](#), [Sections 8.3/8.4](#), and [Section 8.5](#), respectively, and as described in the SoA ([Section 1.3](#)). Note that to ensure study intervention is taken in the morning, clinic visits should take place in the morning.

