8.4. Adverse Events, Serious Adverse Events, and Other Safety Reporting

The definitions of AEs and SAEs can be found in [Appendix 4](#).

Adverse events will be reported by the participant (or, when appropriate, by a caregiver, surrogate, or the participant's legally authorized representative).

The investigator and any qualified designees are responsible for detecting, documenting, and recording events that meet the definition of an AE or SAE and remain responsible for following up all AEs (see [Section 8.4.3](#)).

The method of recording, evaluating, and assessing causality of AEs and SAEs and the procedures for completing and transmitting SAE reports are provided in [Appendix 4](#).

8.4.1. Time Period and Frequency for Collecting Adverse Event and Serious Adverse Event Information

All AEs and SAEs will be collected from the start of intervention until the Safety Follow-up Visit at the time points specified in the SoA ([Section 1.3](#)).

Note: All SAEs that occur after the ICF is signed but before study intervention/treatment must be reported by the investigator if they cause the participant to be excluded from the study or if they are the result of a protocol-specified intervention, including but not limited to washout or discontinuation of usual therapy, diet, placebo treatment, or a procedure.

Medical occurrences that begin before the start of study intervention but after obtaining informed consent will be recorded as Medical History/Current Medical Conditions, not as AEs.

All SAEs will be recorded and reported to the sponsor or designee within 24 hours of first knowledge of the event by study personnel, as indicated in [Appendix 4](#). The investigator will submit any updated SAE data to the sponsor within 24 hours of it being available.

Investigators are not obligated to actively seek information on AEs or SAEs after conclusion of the study participation. However, if the investigator learns of any SAE, including a death, at any time after a participant has been discharged from the study, and he/she considers the event to be reasonably related to the study intervention or study participation, the investigator should promptly notify the sponsor.

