#### **Derivations and Definitions:**

AEs will be collected and reported from the start of study treatment up to the Safety Follow-up visit (approximately 14 days after the last dose of study treatment).

A treatment-emergent adverse event (TEAE) is defined as any AE that began on or after the first dose of study treatment until up to 14 days after the last dose of study treatment.

Adverse events of special interest (AESI) are AEs that are of scientific and medical concern specific to JZP385, which includes hallucination, and syncope. The groupings are defined using MedDRA terms, SMQs (standardized MedDRA queries) and PTs.

Time of first onset of AE is calculated as: TEAE start date – First dose date + 1 and is categorized as:

- Week 1 and 2 ( $1 \leq \text{day of first onset of AE} \leq 14$ )
- Week 3 ( $15 \leq \text{day of first onset of AE} \leq 21$ )
- Week 4 ( $22 \leq \text{day of first onset of AE} \leq 28$ )
- Week 5 ( $29 \leq \text{day of first onset of AE} \leq 35$ )
- Weeks 6 – 17 ( $36 \leq \text{day of first onset of AE} \leq 119$ )
- > Week 17 ( $120 \leq \text{day of first onset of AE}$ )

Incomplete AE start/stop date will be imputed according to Section 6.1.

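### An Efficacy Follow-up Visit may double as the Safety Follow-up Visit with no minimum gap after the last dose, so AE/SAE collection can end 1 to 13 days after dosing instead of 2 weeks

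*Protocol*

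**What the plan says.** Protocol Section 7.1.1 covers participants who stop study intervention but stay in the study. Its default is: "Participants should be scheduled for the Safety Follow-up Visit 2 weeks after the last dose of study intervention". It then adds an exception: "1 of the Efficacy Follow-up Visits can be combined with the participant's Safety Follow-up Visit", allowed "if the Efficacy Follow-up Visit is scheduled to occur within 2 weeks after the" last dose. That sets an upper limit on the gap and no lower limit. For someone who stops between the Week 13 and Week 17 visits, "it is encouraged to schedule an additional Efficacy Follow-up Visit at 17 weeks after first dose".

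Two other places give the 2-week timing without mentioning the exception. Section 4.1 states: "A 2-week Safety Follow-up Period (with visit planned at the end of the 2-week period) will be required for participants who either discontinue early". Footnote b of the Schedule of Activities (Section 1.3) states: "The Safety FU Visit should occur 2 weeks after the E/D visit". The footnote counts from the early discontinuation (E/D) visit, whereas Section 7.1.1 counts from the last dose.

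Section 8.4.1 fixes the end of safety collection: "All AEs and SAEs will be collected from the start of intervention until the Safety Follow-up Visit". It also says investigators need not actively look for events once participation is over.

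SAP Section 4.6.2 counts an adverse event as treatment-emergent from the first dose "until up to 14 days after the last dose of study treatment", and describes the Safety Follow-up visit as falling about 14 days after the last dose. SAP Section 4.1.1.3 closes the Safety Follow-up Period on the day that visit is completed.

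**The concern.** The end of AE collection is tied to a visit rather than to a number of days since the last dose, and Section 7.1.1 lets that visit come early. The SAP's 14-day window would then be only partly observed for some participants, and an event in the unobserved part would look the same as no event.

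Those affected are early discontinuers, who include people stopped for an adverse event or for suicide risk (Section 7.1). Section 8.3.6 asks for close observation around the end of treatment in particular, and the SAP names hallucination and syncope as events of special interest. If late stopping differed between arms, the under-collection would differ too; the documents give no rate from which to judge that.

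**Working it through.** **Inputs.** Week 17 is Day 119 and the Safety Follow-up Visit is Day 133 (Schedule of Activities). Weeks 9 and 13 are Days 63 and 91. Planned safety follow-up is 14 days (Sections 4.1 and 7.1.1).

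**The plan's own figures.** 119 + 14 = 133, matching the scheduled Week 19 visit. Screening 4 weeks + treatment 17 + safety follow-up 2 = 23 weeks, matching the stated maximum. For a completer the 2 weeks are intact.

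**Combined visit at Week 17.** Let s be the last-dose day. Collection after the last dose lasts 119 − s days, and the shortfall is 14 − (119 − s).

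| Last dose (s) | Collection after last dose | Shortfall |
|---|---|---|
| Day 105 | 14 days | 0 |
| Day 108 | 11 days | 3 |
| Day 112 | 7 days | 7 |
| Day 115 | 4 days | 10 |
| Day 118 | 1 day | 13 |

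The clause applies to last doses on Days 105 to 118. Only Day 105 gets the full period. Days 106 to 118 get 1 to 13 days, a mean of (1 + … + 13)/13 = 7. If a safety visit 3 days early counts as ordinary tolerance (an assumption, taking the −3 day window to apply to it), the shortened cases are gaps of 10 days or less, that is, last doses on Days 109 to 118.

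**Weeks 9 and 13.** The same arithmetic gives 1 to 13 days for last doses on Days 50 to 62 (combined on Day 63) and Days 78 to 90 (combined on Day 91). The problem is milder here. Day 14 after those doses falls on Days 64 to 76 and 92 to 104, inside the SAP's analysis windows of 49–76 and 77–104 (SAP Table 7). A combined visit moved to day 14 would still count as the Week 9 or Week 13 efficacy visit. At least one more Efficacy Follow-up Visit is also offered afterwards. However, the AE row of the Schedule of Activities appears to have no mark in the Efficacy Follow-up column, so that later visit does not clearly collect AEs as written.

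**Does anything restore day 14?** I found no such text. Section 8.4.3 follows known SAEs to resolution or stabilization, and Section 8.4.1 has the investigator report related SAEs learned of later. Neither actively collects new events.

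**Illustrative size (assumption).** Take 32 treatment stops (20% of 160) spread evenly over 118 possible days, with every site using the option. Week 17: 32 × 13/118 = 3.5 participants, or 32 × 10/118 = 2.7 with the 3-day tolerance. All three visits: 32 × 39/118 = 10.6, most of them at the two visits where the site can avoid the loss. The 20% is the plan's dropout assumption, not a rate of treatment discontinuation, and neither even timing nor full use of the option is stated anywhere.

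**The case against.** The strongest reply is that this is a deliberate, optional exception to spare participants a clinic visit. Section 7.1.1 states the rule and then relaxes it; Section 4.1 and footnote b give the default. That reading is fair, and the option itself is sensible. It does not follow that AE collection has to stop when the visits are merged, and the proposed change keeps the merger.

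Safety is also partly covered. Every early discontinuer has an E/D visit as soon as possible after stopping, with physical examination, laboratory tests, ECG, vital signs, C-SSRS and AE review. The SAP's 14 days is an upper limit, and the safety analyses are descriptive. All of this stands, and it is why the effect is small.

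A reader might go further and infer that late discontinuers face a scheduling conflict, with no single date able to serve both visits. The documents do not support that. It requires applying the narrow −3/+2 day visit window to both visits, and the columns that window covers cannot be confirmed from the table as available. The SAP's Week 17 window for TETRAS and CGI-S runs from Day 105 to the end of the Maintenance Period, with no numeric upper day. After a last dose on Days 106 to 118 the E/D assessments also fall on or after Day 105 and are eligible for visit mapping (SAP Section 4.1.2). A site can therefore hold Week 17 efficacy data and leave the safety visit at day 14.

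Nor should 13 of 118 calendar days (11.0%) be read as a share of participants. Stops may cluster early: Section 4.2 reports that AEs in the earlier essential tremor study arose mostly in the first week.

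**Conclusion.** The gap is real and minor. As written, a participant using the combined-visit option can have 1 to 13 days of AE/SAE collection after the last dose instead of 2 weeks. The clearest case is a last dose on Days 106 to 118 combined with Week 17, because nothing scheduled follows.

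What is at risk is mainly new non-serious events up to day 14, probably in a few participants. That size rests on the even-timing illustration above; the documents allow no firm count. The option is permissive, so the loss can happen but need not. A reader might infer that SAEs go unreported or that the primary result is affected. The first is limited by the SAE follow-up and later-notification rules, and the second does not follow: the clause changes neither the Week 17 efficacy assessment nor the power.

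**What to change.** Keep the option to combine. Add one sentence to each of Sections 7.1.1 and 8.4.1: if the combined visit falls before day 14 after the last dose, allowing the normal visit window, AE/SAE collection continues to day 14. It would be completed by one phone contact, or at a later Efficacy Follow-up Visit on or after day 14. For the second route, mark AE collection in the Efficacy Follow-up column of the Schedule of Activities.

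The SAP needs no change, since it already classifies treatment-emergent events by date to 14 days after the last dose. The cost is at most one phone contact per affected participant, with no extra clinic visit and no shift in the Week 17 efficacy assessment.

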7.1.2. Positive Alcohol or Urine Drug Screens

Participants must abstain from alcohol at least 12 hours prior to each clinic visit. The investigator may discontinue study intervention for any participant with a positive alcohol or urine drug screen. However, if the investigator believes discontinuation of study intervention is not necessary despite a positive alcohol or urine drug screen result, approval from the Sponsor Medical Monitor is required to retain the participant in the study. If the investigator suspects a false positive urine drug screen, he/she is encouraged to send a portion of the same urine sample to the central laboratory for confirmatory testing (eg, GCMS).

7.1.3. Temporary Discontinuation/Study Intervention Interruption

If a participant must temporarily interrupt study intervention for any reason, the Medical Monitor should be consulted to determine whether the participant will resume study intervention.

7.2. Participant Discontinuation/Withdrawal from the Study

- A participant may withdraw from the study at any time at his/her own request or may be withdrawn at any time at the discretion of the investigator for safety, behavioral, or compliance reasons.
- At the time of discontinuing from the study, an E/D Visit should be conducted. In addition, a Safety Follow-up Visit should be conducted as shown in the SoA ([Section 1.3](#)). See the SoA for data to be collected at the time of study discontinuation and at the Safety Follow-up Visit and for any further evaluations that need to be completed. The participant will be permanently discontinued both from the study intervention and from the study at that time.
- If the participant withdraws consent for disclosure of future information, the sponsor may retain and continue to use any data collected before such a withdrawal of consent.
- If a participant withdraws from the study, he/she may request destruction of any samples taken and not tested, and the investigator must document this in the site study records.

7.3. Lost to Follow-up

A participant will be considered lost to follow-up if he or she repeatedly fails to return for scheduled visits and is unable to be contacted by the study site.

The following actions must be taken if a participant fails to return to the clinic for a required study visit:

- The site must attempt to contact the participant and reschedule the missed visit as soon as possible.
- The site must counsel the participant on the importance of maintaining the assigned visit schedule and ascertain whether or not the participant wishes to and/or should continue in the study.

- Before a participant is deemed lost to follow-up, the investigator or designee must make every effort to regain contact with the participant (where possible, 3 telephone calls and, if necessary, a certified letter to the participant's last known mailing address or local equivalent methods). After trying to contact the participant, the investigator should reach out to the contact provided by the participant. These contact attempts should be documented in the participant's medical record.
- Should the participant continue to be unreachable, he/she will be considered to have withdrawn from the study and lost to follow-up.

Discontinuation of specific sites or of the study as a whole are handled as part of [Study and Site Start and Closure \(Section 10.1.9\)](#).

8. STUDY ASSESSMENTS AND PROCEDURES

- Study procedures and their timing are summarized in the SoA ([Section 1.3](#)).
- For clinic visits, participants should be admitted to the study site in the morning. The investigator may opt to have the participant attend an unscheduled visit, if deemed necessary, at any time during the study. Some clinic visits may be conducted remotely, if required due to the coronavirus 2019 pandemic, and with approval from the Sponsor Medical Monitor, as noted in the SoA.
- Immediate safety concerns should be discussed with the sponsor immediately upon occurrence or awareness to determine if the participant should continue or discontinue study intervention.
- Adherence to the study design requirements, including those specified in the SoA, is essential and required for study conduct.
- All Screening evaluations must be completed and reviewed to confirm that potential participants meet all eligibility criteria. The investigator should maintain a screening log to record details of all participants screened and to confirm eligibility or record reasons for screening failure, as applicable.
- After Screening procedures have been completed and eligibility criteria have been confirmed, the investigator should provide eligible participants with instructions on how to discontinue any excluded medication(s). Document that the investigator has determined that discontinuation is safe and medically appropriate, and the discontinuation is medically supervised. The Sponsor Medical Monitor should be contacted if there are any questions regarding discontinuation of excluded medication(s).
- [REDACTED]
- [REDACTED]
- The maximum amount of blood collected from each participant over the duration of the study, including any extra assessments that may be required, will not exceed 125 mL (see Laboratory Manual). Repeat or unscheduled samples may be taken for safety reasons or for technical issues with samples.
- For clinical outcome assessment measures that are rated by specially qualified and trained interviewers/raters, the same person should perform each assessment for the same participant throughout the duration of the study, whenever possible.
- The TETRAS-PS assessment will be administered and scored by a blinded trained rater at the site throughout the study. Blinded raters are defined as clinical site personnel who have undergone the required training in administration and scoring of the TETRAS-PS. The blinded rater who rates the TETRAS-PS for a participant may not rate/administer other scales for that participant nor be involved in other procedures for that participant. Blinded raters must not share any information they collect about participants with other site staff, except when required to ensure participant safety. Appropriate training for rating scales will be provided by the rater

training vendor. Documentation of how and when data are filed, stored, and transmitted to or from the study site will be provided in the Trial Site Binder.

